6.2 Secondary Objectives

Objectives	Endpoints/Variables
Complete Response Rate (CR+CRi)	
To estimate the preliminary antitumor activity of AZD0466 by assessment of Complete response rate (CR+CRi) in patients with advanced haematological malignancies	
Complete response rate (CR+CRi) is defined as the proportion of patients who have a complete remission (CR) or incomplete haematological response (CRi), as determined by criteria described in Appendix J and Appendix K of the study protocol.
 
The analysis will include all dosed patients as intended.
 
Data obtained from first dose up until progression, or the last evaluable assessment in the absence of progression, will be included in the assessment of CR+CRi, regardless of whether the patient withdraws from study treatment. Patients who go off treatment without a response or progression, receive a subsequent therapy, and then respond will not be included as responders in this evaluation.
 
The measure of interest is the estimate of CR+CRi.

Time to Response (TTR)	
To estimate the preliminary antitumor activity of AZD0466 by assessment of time to complete	Time to response is defined as the time from date of first dose until the date of first documented CR or CRi.

Objectives	Endpoints/Variables
response (TTR) in patients advanced haematological malignancies	
The analysis will include all dosed patients as intended, who have a complete remission. Patients who go off study treatment without a clinical response and receive a subsequent therapy and then respond will not be included. The measure of interest is median TTR.

Duration of Response (DoR)	
To estimate the preliminary antitumor activity of AZD0466 by assessment of DoR in patients with advanced haematological malignancies.	
DoR will be defined as the time from the date of first documented response (CR+CRi) until date of documented progression, relapse, failure (relapse and failure as determined by criteria described in Appendix J and Appendix K of the study protocol) or death due to any cause. The analysis will include all dosed patients as intended who have a confirmed response (CR or CRi), regardless of whether the patient withdraws from study treatment or receives another anticancer therapy. The measure of interest are the percentiles of DoR.

Overall Survival (OS)	
To estimate the preliminary antitumor activity of AZD0466 by assessment of OS in patients with advanced haematological malignancies.	
OS is defined as time from date of first dose until the date of death due to any cause. The comparison will include all dosed patients as intended, regardless of whether the patient withdraws from therapy or receives another anticancer therapy. The measures of interest are the median OS and landmarks at 6 and 12 months of OS.

ALL, acute lymphocytic leukaemia; AML, acute myeloblastic leukaemia; CR, complete remission; CRi, incomplete haematological response; DoR, duration of response; OS, overall survival; TTR, time to response

6.3 CCI

CCI	CCI
CCI	CCI

[figure not shown]
7 INVESTIGATIONAL PLAN - Module 1 Part A

7.1 Overall Study Design

Module 1 Part A is a Phase I dose escalation evaluation of AZD0466 monotherapy.

A visual representation of Module 1 is shown in [Figure 1](#).

Figure 1 Schema for Module 1

^a AZD0466 doses shown are illustrative. Actual doses will not exceed a 2-fold increase of a dose declared tolerable by the SRC, or the maximum feasible dose as specified in the study protocol section 11.4.7.5.

Dotted paths contingent on emerging data.

ALL, acute lymphoblastic leukaemia; AML, acute myeloid leukaemia; DL, dose level; IA, interim analysis; MPN, myeloproliferative neoplasm; TP53, gene encoding tumour protein p53.

Part A, the dose escalation part of the study, will enrol up to 40 patients with a histologically confirmed AML or ALL to ensure 30 DLT-evaluable patients in total. At least 3 DLT-evaluable patients are required at each dose level and, up to 12 patients overall may be enrolled at each dose level. Up to additional 18 patients may be enrolled to backfill earlier cohorts at lower dose levels with the intent of enabling pre- and on-treatment peripheral blood samples and bone marrow aspirates and biopsies to aid characterisation of the PD of AZD0466 and to provide additional data on safety, tolerability, PK, and biological activity (n = 58 in total). If a dose escalation cohort and a backfill expansion cohort are simultaneously open to enrolment, precedence will be given to enrolment into the dose escalation cohort.

A SRC will be responsible for making recommendations for dose-escalation or de-escalation after each dose level, including decisions on opening cohorts for backfill, in accordance with the SRC charter. From day of target dose, a delay of at least 3 days will be mandatory between the first and second patient at each dose level. This separation between the dosing of patients will ensure that any acute toxic effects of the AZD0466 infusion will have sufficient time to be identified before additional patients are exposed. The intra-patient dose ramp-up and/or dose schedule for each cohort may be modified based on safety, PK, and PD findings of a previous dose level. The SRC will also assess all evaluable patients to establish the recommended Phase II dose (RP2D) and determine if the study should progress to Part B.

7.2 Endpoints and Associated Variables

7.2.1 Efficacy Variables

For the definitions of the efficacy variables for the response evaluation criteria variables for ALL and AML, and extramedullary disease refer to the Section 3.2.1.

7.2.1.1 Overall Survival (OS)

OS is defined as the time from date of first dose until the date of death from any cause. The analysis will include all dosed patients according to assigned dose, regardless of whether the patients withdraws from therapy or received another anticancer therapy. Patients who have not died during the course of the study will be censored at their last date known to be alive.

Survival follow-up phone calls or clinic visits will be made approximately every 1 month after last dose for all patients for survival until death, lost to follow-up, AstraZeneca closes the study or withdrawal of consent, whichever occurs first. The status of ongoing, withdrawn (from the study) and “lost to follow-up” patients at the time of the final OS analysis should be obtained by the site personnel by checking the patient’s notes, hospital records, contacting the patient’s general practitioner and checking publicly available death registries. In the event that the patient has actively withdrawn consent to the processing of their personal data, the vital status of the patient can be obtained by site personnel from publicly available resources where it is possible to do so under applicable local laws.

For any OS analysis performed prior to the final OS analysis, in the absence of survival calls being made, it is necessary to use all relevant eCRF fields to determine the last recorded date on which the patient was known to be alive for those patients still on treatment (since SURVIVE module is only completed for patients off treatment if a survival sweep is performed). The last date for each individual patient is defined as the latest among the following dates recorded in the eCRF:

- AE start and stop dates
- Admission and discharge dates of hospitalisation
- Study treatment date
- End of treatment date
- Laboratory test dates
- Date of vital signs
- Disease assessment dates on eCRF
- Start and stop dates of alternative anticancer treatment
- Date last known alive on survival status eCRF
- End of study date.

7.2.1.2 Peripheral Blood

Peripheral blood will be collected for complete blood count (CBC) (laboratory safety assessment) as indicated in the SoA in Tables 14, 15 in the study protocol. CCI

7.2.1.3 Extramedullary Disease

Refer to Section 3.2.1.2.

7.2.1.4 Bone Marrow

Bone marrow core biopsy and bone marrow aspirate should be performed as specified in the SoA in Tables 16, 17 in the study protocol.

- Screening (between Day -14 and -1)
- Cycle 1 Day 30 ± 1 day
- Cycle 2 and subsequent cycles between Days 23 to 28
- Disease progression or EoT visit

The disease progression sample collection may occur at the safety follow-up visit (if conducted in person) if not collected previously. Additional bone marrow or peripheral blood samples may be collected, as clinically indicated.

7.2.2 Pharmacokinetic Variables

Pharmacokinetic parameters will be calculated by non-compartmental analysis methods using Phoenix® WinNonlin® (Version 8.1) or higher as data applicable.

The PK parameters are calculated/estimated according to AstraZeneca standards.

PK analysis will, where data allow, be carried out using actual elapsed times determined from the PK sampling and dosing times recorded will be used in the database. If actual elapsed times are missing, nominal times may be used. Nominal sampling times may be used for any agreed interim PK parameter calculations and PK parameters will be derived using standard non-compartmental methods.

Where data allow, the following PK parameters for total and released AZD4320 will be derived from plasma concentrations supporting doses on Cycle 1 Day 8 and Cycle 2 Day 1.

Plasma

C_{\max}	Maximum observed plasma (peak) drug concentration
t_{\max}	Time to reach peak or maximum observed concentration or response following drug administration
λz	Terminal rate constant, estimated by log-linear least squares regression of the terminal part of the concentration-time curve
$t_{1/2} \lambda z$	Half-life associated with terminal slope (λz) of a semi-logarithmic concentration-time curve
AUC_{0-72}	Partial area under the plasma concentration-time curve from time 0 to 72 hours after the start of infusion (Cycle 1 Day 8 only)
AUC_{0-36}	Partial area under the plasma concentration-time curve from time 0 to 36 hours after the start of infusion (to match urine collection interval) (Cycle 1 Day 8 only)
AUC_{0-24}	Partial area under the plasma concentration-time curve from time 0 to 24 hours after the start of infusion (to support comparisons between C1D8 and C2D1)
AUC_{last}	Area under the plasma concentration-time curve from time 0 to the last quantifiable concentration
t_{last}	Time of last observed (quantifiable) concentration
C_{trough}	Concentration prior to dosing

Dose normalised AUC _{last} ^a	Area under the plasma concentration-time curve from time 0 to time of last quantifiable analyte concentration divided by the administered AZD4320 dose in mg
Dose normalised AUC ₀₋₂₄ ^a	Area under the plasma concentration-time curve from time 0 to 24 hours after the start of infusion divided by the administered AZD4320 dose in mg
Dose normalised AUC ₀₋₇₂ ^a	Area under the plasma concentration-time curve from time 0 to 72 hours after the start of infusion divided by the administered AZD4320 dose in mg (Cycle 1 Day 8 only)
Dose normalised C _{max} ^a	Maximum observed plasma (peak) drug concentration divided by the administered AZD4320 dose in mg

^a Calculated for total AZD4320 only; AZD4320 dose calculated as 29% w/w of the AZD0466 dose in mg, based on average batch results, unless an alternate value is specified.

The following diagnostic parameters for plasma PK analysis will be provided:

λz lower	Lower (earlier) t used for λz determination
λz upper	Upper (later) t used for λz determination
λzN	Number of data points used for λz determination
Rsq	Statistical measure of fit for the regression used for λz determination
Rsq adj	Statistical measure of fit for the regression used for λz determination adjusted for the number of used data points (n obs)

The time period used for the estimation of apparent terminal elimination half-lives, where possible, should be over at least two half-lives. For $t_{1/2}$ estimates where λ_z was calculated over a time period less than twice their resultant half-life, the reliability of $t_{1/2}$ and any PK parameters derived from λ_z will be discussed in CSR.

Urine

Data permitting, the following urine PK parameters will be calculated for total AZD4320 for Cycle 1 Days 1, 4, and 8, as appropriate:

Table 4 Urine PK parameters

Ae(t1-t2)	Cumulative and by interval amount of unchanged drug excreted in urine from time t1 to t2
fe(t1-t2)	Cumulative and by interval percentage of adjusted AZD4320 dose excreted unchanged in urine from time t1 to t2. For fe, adjusted dose will be calculated as (AZD0466 dose / AZD0466 mol weight * AZD4320 mol weight)
CLR	Renal clearance of drug from plasma (Day 8 only)

Additional PK parameters may be calculated as appropriate.

7.2.3 Safety and Tolerability Variables

Part A

The primary objective of Part A is to assess the safety and tolerability, describe the DLTs, and identify the MTD and/or RP2D of AZD0466 in patients with advanced haematological malignancies.

As referenced in Section 3.2.3 the safety assessments performed will be:

- Adverse event (AE) assessments
- Clinical chemistry (including creatine phosphokinase) and haematology as described in Section 4.14.6.
- Amylase and lipase, coagulation indices, serum immunoglobulins, urinalysis, cardiac troponin and BNP (or NTproBNP), clinical and laboratory assessments for TLS, cortisol, ACTH and TSH parameters described in Section 4.14.6.
- Vital signs (systolic blood pressure [SBP] and diastolic blood pressure [DBP], pulse rate, oral body temperature), height and weight
- 12-lead Electrocardiograms (ECG)
- Tumour lysis syndrome (TLS)
- Eastern Cooperative Oncology Group performance status (ECOG PS)
- Left ventricular ejection fraction (echocardiograms [ECHO] / multi-gated acquisition scan [MUGA]).

The full list of laboratory measurements performed during the study that are used to evaluate safety and tolerability variables can be found in [Table 1](#) and [Table 2](#).

8 STATISTICAL METHODS - Module 1 Part A

8.1 Data Quality Assurance

Refer to Section [4.1](#).

8.2 General Presentation Considerations

Refer to Section [4.2](#).

8.3 General Variables

8.3.1 Study Day Definitions

Refer to Section [4.3.2](#).

8.3.2 Time Windows

Refer to Section [4.3.3](#).

8.3.3 Handling of Missing Data

Refer to Section [4.3.4](#).

8.3.4 Imputation Rules for Laboratory Values Outside of Quantification Range

Refer to Section [4.3.5](#).

8.4 Software

Refer to Section [4.4](#).

8.5 Analysis Sets

Details of the analysis sets are presented in [Table 5](#).

Table 5 Analysis Sets – Module 1

Population/Analysis set	Description
Screened	All patients that signed the informed consent form (ICF)
Safety	All patients who received at least one dose of AZD0466
Intention-to-treat	All patients who received at least one dose of AZD0466
Evaluable for Response	All patients who have received at least 3 doses of AZD0466 at the target dose level in Cycle 1
DLT-evaluable	
Patients enrolled in the dose-escalation part of Module 1 that have received at least 3 doses of AZD0466 at the target dose level (75% of target doses from Day 8 to Day 29 in Cycle 1) and have completed the safety follow-up through the 35-day DLT evaluation period
 
Or
 
Have experienced a DLT during the 35-day DLT evaluation period in Cycle 1.

Pharmacokinetics	Dosed patients with at least one reportable plasma concentration and no important AEs or protocol deviations that may impact PK

A summary on which analysis set will be used for each outcome variable is provided in [Table 6](#).

Table 6 Summary of outcome variables and analysis sets

Outcome variable	Analysis Set
Study Population/Demography Data	
Disposition	Enrolled
Demography and baseline characteristics	Safety
Important protocol deviations	Safety
Medical History	Safety
Prior/Concomitant Medication	Safety
Safety data	
Exposure	Safety
Adverse Events	Safety
Laboratory measurements	Safety
Vital Signs/ECG/Physical examination	Safety
ECOG PS	Safety
DLTs	DLT-evaluable
Efficacy Data	
CR rate	Evaluable for response; Intention-to-treat
TTR	Evaluable for response
DoR	Evaluable for response
OS	Intention-to-treat
ORR	Evaluable for response; Intention-to-treat
Pharmacokinetics	
Pharmacokinetic variables	PK

CR complete response; DLT dose-limiting toxicity; DoR duration of response; ECOG PS Eastern Co-operative Oncology Group performance status; OS overall survival; PK pharmacokinetic.

The number of enrolled patients included/excluded from each of the analysis sets will be summarized. Patients and data excluded from each analysis set will be listed with the reason for exclusion.

8.6 Study Patients

8.6.1 Disposition of Patients

Refer to Section 4.6.1.

8.6.2 Protocol Deviations

Refer to Section 4.6.2.

8.7 Demographics and Baseline Characteristics

Refer to Section 4.7.

8.8 Medical/Surgical History

Refer to Section 4.8.

8.9 Concomitant Medications and Other Treatments

Refer to Section 4.10.

8.10 Efficacy Evaluation

The preliminary antitumor activity of AZD0466 will be estimated using the following endpoints:

- Complete response,
- OS.

All of the collected response related data, such as from complete blood count (CBC), extramedullary disease status, bone marrow core biopsy and aspirate will be listed for all patients in the Intention-to-treat analysis set. Summaries will not be produced.

8.10.1 Analysis and Data Conventions

No hypotheses are planned to be tested.

8.10.1.1 Multi-centre Studies

No adjustments for centre will be performed.

8.10.1.2 Adjustments for Covariates

No adjustments for covariates will be performed.

8.10.1.3 Handling of Dropouts or Missing Data

Summary statistics will be based on non-missing values unless otherwise specified.

8.10.2 Primary Efficacy Endpoints

8.10.2.1 Complete Response (CR+CRi) Rate

Complete response rate (CR+CRi) for AML and ALL patients is defined as the proportion of patients with best response as complete remission (CR) or incomplete haematological response (CRi), as determined by criteria described in Section 3.2.1 and in Appendix J and Appendix K in the study protocol. Any treated patient who has not satisfied the criteria for CR or CRi will be treated as a non-responder for this analysis.

Data obtained from first dose up until treatment failure or disease progression, or the last evaluable assessment in the absence of treatment failure or disease progression, will be included in the assessment of CR+CRi, regardless of whether the patient withdrew from study treatment.

The complete response rate will be presented along with all remaining response categories, as defined in Section 3.2.1 by means of the proportion (%).

The analyses will include all patients from the Evaluable for Response analysis set. Patients who went off treatment without a response or who received a subsequent therapy after treatment failure or disease progression, and then respond will not be included as responders in this evaluation.

Secondarily, the analyses will be repeated for the Intention-to-treat analysis set, for that the denominators for the calculation of percentages will refer to the number of patients in the Intention-to-treat analysis set. Patients who are not evaluable for response analysis will not be assigned to a response category and frequencies for missing data items will not be presented.

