9.5 General Considerations

Descriptive statistics will be used for all variables. Continuous variables will be summarised by the number of observations, mean, standard deviation, median, minimum, and maximum. Categorical variables will be summarised by frequency counts and percentages for each category. Unless otherwise stated, percentages will be calculated out of the population total.

All data collected will be listed. Demographic data will be summarised on the safety population set. Exposure data will be summarised on the safety population set. The efficacy endpoints for response will be summarised on the appropriate evaluable for response population set. The efficacy endpoints for OS will be summarised on the intent-to-treat (ITT) population set (Section 11.7.3). Safety data will be summarised on the safety population set (Section 11.7.3).

Demographic data

Characteristics of the patients, including medical history and disease characteristics at baseline will be listed for each patient and summarised by dose group where appropriate. Reasons for discontinuation of study treatment will be listed including the study day of treatment discontinuation and will be summarised by dose group if appropriate.

Exposure

Exposure to study treatment ie, total amount of study drug received will be listed for all patients. Total exposure and total time on study (date of last dose minus date of first dose) will be summarised by the following: mean, standard deviation, minimum, maximum, median and

number of observations.

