11.7.2.2 Part B Monotherapy Dose Expansion

Separate expansion cohorts will enrol 4 distinct populations of patients with advanced haematological malignancies. Three of these expansion cohorts (Expansion Cohorts B1, B2, and B4) will recruit at least 21 patients, and one (Expansion Cohort B3) will recruit at least 25 patients. The total number of patients treated in Part B will be at least 88. These sample sizes have been determined to ensure confidence intervals constructed around the complete response rate (CR+CR_i), as calculated after all patients have had the opportunity to complete one treatment cycle, will provide sufficient information to enable decisions to be made around the likely success of future studies in these patient populations, using methodology described in [Frewer et al 2016](#).

Thresholds for decision making were set for each expansion cohort based on range of literature and expert opinion. For Expansion Cohort B1, a target value for response was set at 35%, with a lower reference value of 20%. If 7 or more responders are observed from 21 patients, there will be at least an 80% chance that the true response rate is at least 20%, which may promote a positive decision. If 4 or fewer responders are observed, then there is a 10% or less chance that the true rate is at least 35%, which may lead to a futility decision. If

the true rate of response is 15%, then, with 21 patients, there is an 80.3% probability of a result that may trigger a decision to stop further development in this population due to futility. This analysis will be performed using the ITT population.

An IA as described in Section 11.7.9 will be performed in each expansion cohort when 12 patients have had the opportunity for one cycle of treatment and is response evaluable as per [Table 21](#). The number of patients is based on the operating characteristics of the cohort-specific decisions using the approach as described in [Frewer et al 2016](#).

In Expansion Cohort B1, if 5 or more responders are observed from 12 patients, then there is at least an 80% chance that the true response rate is at least 20%, which may promote a decision to continue to full recruitment. It may be considered futile to continue development of this cohort if there is < 10% probability for the response rate to be greater than 35%. This translates to observing one or zero responders out of 12 patients.

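### SAP 8.10.2.1 presents the CR+CRi rate first on patients with three or more target doses, although the endpoint is defined on all dosed patients and the non-responder rule covers every treated patient

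*SAP*

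**What the plan says.** SAP 8.10.2.1 defines the complete response rate for AML and ALL patients and sets a non-responder rule: "Any treated patient who has not satisfied the criteria for CR or CRi will be treated as a non-responder for this analysis". It then names the analysis set: "The analyses will include all patients from the Evaluable for Response analysis set". SAP Table 5 admits a patient to that set only after three or more target doses in Cycle 1. The all-dosed result comes next: "Secondarily, the analyses will be repeated for the Intention-to-treat analysis set", with percentages taken over the ITT number. ITT in Table 5 means one dose or more. For this repeat the SAP adds "Patients who are not evaluable for response analysis will not be assigned to a response category". It also leaves out the counts of missing responses: "frequencies for missing data items will not be presented".

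The endpoint definition in SAP 6.2 says of CR+CRi: "The analysis will include all dosed patients as intended". Protocol Table 13 uses the same sentence. Protocol 9.5, in the core statistical section, points the other way: "The efficacy endpoints for response will be summarised on the appropriate evaluable for response population set". SAP Table 6 lists both sets for the CR rate, the evaluable set first.

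SAP Section 13 says that the protocol 11.7.6 analyses, written for Part B, will be applied to Part A if data allow. Protocol 11.7.6 repeats the any-treated-patient rule and names no analysis set. Section 13 does not say which set Part A follows.

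**The concern.** A treated patient with fewer than three target doses cannot be counted as a non-responder in a denominator that leaves that patient out. The rule and the set in SAP 8.10.2.1 therefore do not fit together, and the set does not match the population in SAP 6.2 and Table 13.

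The patients left out are not a random subset. They include those who progressed, died or stopped treatment early, so membership of the evaluable set depends on what happened after dosing began. SAP 8.10 names only complete response and OS as efficacy endpoints for Part A. The first CR+CRi figure in the study report is the one most likely to be quoted as the activity estimate, and it would rest on patients who stayed on treatment long enough to qualify.

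The ITT repeat has a gap of its own. It does not define which patients are not evaluable for response analysis, and it gives those patients no row.

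**Working it through.** **1. When a patient becomes evaluable.** Target doses fall on Days 8, 15, 22 and 29 of Cycle 1 (protocol 11.4.1 and 11.4.7.1). On schedule, the third is on Day 22. The first scheduled on-treatment marrow is Day 30 ± 1 (SAP 7.2.1.4). A patient who fails before Day 22 leaves the evaluable set before any scheduled marrow assessment.

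**2. Nearest planning figure.** Neither document gives a response-evaluable number. For DLT evaluability, protocol 11.1.3.2 plans up to 48 patients for about 36 evaluable: 1 - 36/48 = 25%, and 36/(1 - 0.25) = 48. SAP 7.1 has 40 for 30: 1 - 30/40 = 25%, and 30/(1 - 0.25) = 40. Both reproduce. The 25% is only a proxy, because the DLT-evaluable set also admits patients with a DLT at any dose count and otherwise requires follow-up through the DLT period.

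**3. Effect on the rate.** Let N be the dosed patients, R the responders, f the share of N outside the evaluable set, and s the share of R among those patients.

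- All-dosed rate = R/N
- Evaluable rate = (1 - s)R / ((1 - f)N)
- Ratio = (1 - s)/(1 - f), above 1 only when s < f

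| Assumed f | s = 0 | s = f/2 | s = f |
|---|---|---|---|
| 10% | 1/0.90 = 1.11 | 0.95/0.90 = 1.06 | 1.00 |
| 25% | 1/0.75 = 1.33 | 0.875/0.75 = 1.17 | 1.00 |
| 40% | 1/0.60 = 1.67 | 0.80/0.60 = 1.33 | 1.00 |

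At an assumed all-dosed rate of 20% with s = 0, the evaluable rate is higher by 2.2, 6.7 and 13.3 percentage points.

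**4. Illustration.** Take 8 responders (assumed), all evaluable, with 48 dosed and 36 evaluable. The evaluable rate is 8/36 = 22.2% (exact 95% CI 10.1 to 39.2). The all-dosed rate is 8/48 = 16.7% (7.5 to 30.2).

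**5. The ITT repeat, on two readings of not evaluable.**

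- *Outside the Evaluable for Response set.* Early progressions and deaths get no category, and a CR or CRi after fewer than three target doses is not counted. The repeat then shows (1 - s) times the true all-dosed rate: 0.95, 0.875 and 0.80 at s = f/2 for the three values of f.
- *Without a response assessment.* SAP 3.2.1.1 and 3.2.1.2 still place early failures in categories such as treatment failure or death from indeterminate cause, and all documented responses count.

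On either reading, patients left without a category have no row, so the percentages need not sum to 100%.

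**The case against.** The best defence is that the SAP follows the protocol. Protocol 9.5 is the core section that assigns analysis sets, and it gives response to the evaluable set and OS to ITT. Following it is not obviously a change to the planned analysis. This stands: the protocol is divided, and the SAP choice has a source.

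The non-responder sentence could also be read as applying within whichever set is being analysed, and the ITT run satisfies it literally. That reading is possible, but SAP 6.2 and Table 13 still say all dosed patients. Restricting those passages to the evaluable set would also restore consistency, but it would keep the selection on early outcome.

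Three stronger inferences are tempting, and the documents do not support them.

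- *The all-dosed result is lost or early failures are hidden.* The ITT rate is pre-specified with its own denominator. SAP 8.5 counts inclusions and exclusions for each set and lists exclusions with reasons. Disposition, deaths and the ITT listings show early failures.
- *The protocol requires ITT for Part A because it does so for Part B.* Protocol 11.7.2.2 says "This analysis will be performed using the ITT population", and 11.7.5 agrees for fully recruited cohorts. However, these rules are for Part B, which was not opened, and 11.7.9 uses the evaluable set at the 12-patient interim. They do not govern Part A.
- *The first rate is certainly inflated.* It is not if s is at least f. A patient with withheld doses can miss the third target dose, still reach a marrow assessment, and respond.

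Finally, SAP version 2.0 is dated December 2023, after the planned last visit of August 2023 in an open-label study, so reordering the sets now is itself a late choice. That is a reason to record it and keep both rates. It does not justify leaving the mismatch.

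**Conclusion.** The inconsistency is real and minor. The first-presented CR+CRi rate uses a narrower population than the endpoint definition, and that population is selected on early outcome. The likely bias is upward. Its size depends on f and s, which the documents do not give: from none (s = f) to a factor of 1.33 at f = 25% with every responder evaluable, or 1.67 at f = 40%. The 25% is a DLT planning proxy; the 20% rate and the 8 responders are illustrations.

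No hypothesis is tested and the ITT rate is still reported. The consequence is a descriptive estimate that can be misread. In the ITT repeat, an undefined term could drop some responses, and uncategorised patients have no row.

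**What to change.** - **SAP 8.10.2.1 and Table 6:** present CR+CRi first on all dosed AML/ALL patients, with the Evaluable for Response set as supportive. State this denominator explicitly, because 8.10.2.1 defines the rate for AML and ALL, whereas ITT is every dosed patient and Part A admits MDS.
- **Counting rule:** keep the existing data window (first dose up to treatment failure or progression) and the exclusion of responses after subsequent therapy. Within it, count a documented CR or CRi whatever the number of target doses, and everyone else in the denominator as a non-responder.
- **ITT paragraph:** replace the sentence that leaves patients uncategorised and suppresses missing frequencies with a Not evaluable row for patients with no response assessment, so that the categories sum to 100%.
- **SAP Section 13:** record that protocol Table 13 is followed over protocol 9.5 for Part A.

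The cost is SAP wording, one Table 6 entry, one table row and one line in Section 13. No new data are needed. The first-presented rate may be slightly less favourable.
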